4.6.2 Handling missing efficacy data

Missing data can result from patients discontinuing the study prematurely or by missing intermediate visits or selected assessments while remaining in the study. To eliminate missing data, every effort will be made to obtain the protocol-required data for all scheduled study assessments for all enrolled patients. For efficacy analyses, the MMRM model assumes missing observations are missing at random (MAR). MAR means that the tendency of a data value to be missing depends only on the observed data, and not on the missing data. For example, if an HbA1c value is missing, it assumes this is not related to the missing data but to some of the observed data (response and covariates) (Ref (1)).

For the change in HbA1c and weight analyses using MMRM, values recorded after rescue treatment for those patients who used rescue medication or values collected more than 8 days after the last dose date for patients who stayed more than 8 consecutive days off treatment are excluded from the analysis. For the change in FPG analysis using MMRM, values recorded after rescue treatment for those patients who used rescue medication or values collected more than 1 day after the last dose date for patients who stayed more than 1 consecutive days off treatment are excluded from the analysis. For the change in SBP analysis using MMRM, values recorded after rescue treatment for those patients who used rescue medication or values collected more than 4 days after the last dose date for patients who stayed more than 4 consecutive days off treatment are excluded from the analysis.

The MMRM model assumes the time course of the endpoint values for patients who discontinue double-blind treatment or are rescued at a specific time point is consistent with the time course for patients ongoing at that time point.

Summaries of missing data by visit for HbA1c will be provided in order to explore this assumption (see Table 16 provided in Appendix IV).

When performing ANCOVA, the Last Observation Carried Forward (LOCF) method will be used for dealing with missing values i.e. if no Week 52 measurement is available, the last available earlier post-baseline measurement will be used except for the efficacy variable time spent below HbA1c target. For patients who started rescue medication prior to Week 52, their last post-baseline measurement taken prior to the date of the first dose of rescue medication will be used.

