4.8.2 Analysis of secondary and exploratory variables

All secondary endpoints will be analysed using the Full Analysis set including values prior to rescue treatment or discontinuation. For HbA1c, weight, BMI and waist circumference, values recorded after rescue treatment for those patients who used rescue medication or values collected more than 8 days after the last dose date for patients who stayed more than 8 consecutive days off treatment are excluded from the analysis. For FPG, values recorded after rescue treatment for those patients who used rescue medication or values collected more than 1 day after the last dose date for patients who stayed more than 1 consecutive day off treatment are excluded from the analysis. For SBP, values recorded after rescue treatment for those patients who used rescue medication or values collected more than 4 days after the last dose date for patients who stayed more than 4 consecutive days off treatment are excluded from the analysis.

The statistical testing of the primary and key secondary efficacy variables will proceed in a sequential manner. If for the primary comparison between dapagliflozin or dapagliflozin plus saxagliptin (added to metformin) treatment group and the glimepiride (added to metformin) treatment group, the upper limit from a 2-sided 95% CI for the difference in adjusted means is less than 0.30%, then the dapagliflozin or dapagliflozin plus saxagliptin will be non-inferior to glimepiride and all four key secondary efficacy variables will be tested for superiority at a 0.05 level (two-sided) as well as the superiority test of the primary efficacy variable. To protect the type I error rate of the hierarchical testing procedure, the interpretation of the statistical significance of treatment comparisons for each key secondary efficacy variable and the superiority test of the primary efficacy variable will be done using a step-wise procedure (described in Section 4.3.1).

A summary of each efficacy variable and associated analysis is provided in Table 11.

The analysis of the changes from baseline to week 52 for a) total body weight, b) FPG and c) SBP will be performed using the MMRM model (as described for the primary efficacy endpoint). Point estimates and 2-sided 95% CI will be calculated for the adjusted mean changes from baseline within each treatment group and between treatment groups together with the p-values corresponding to testing the hypotheses of no difference between

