dapagliflozin added to metformin and dapagliflozin plus saxagliptin added to metformin compared to glimepiride added to metformin.

The time spent below HbA1C target (<7% and <7.5%) from baseline to week 52 will be analysed using an analysis of covariance (ANCOVA) model with fixed effects for treatment group and baseline HbA1c (see section 4.5.5). The change from baseline at week 52 in a) BMI and b) waist circumference will be analysed using an ANCOVA model with fixed effects for treatment groups and respective baseline covariates (see section 4.5.5). LOCF will be applied as detailed in section 4.6.2 for the latter two analyses. The ANCOVA model will be used to derive a least squares estimate of each test drug combination versus the control with 95% CI and (a corresponding 2-sided) p-value. In addition, a 2-sided 95% CI for the mean change within each treatment group will be calculated.

Time to rescue will be analysed using a Cox proportional hazards model with the Efron method (Ref 2) for handling ties (i.e., same rescue times). Estimates of the hazard ratio and 95% CI will be provided. Kaplan-Meier estimates will be calculated and plotted by treatment group. Median time to rescue and their 95% CIs (derived from the Kaplan-Meier estimates) will also be reported. Patients will be censored at the final visit (Visit 12; week 52) if rescue has not occurred by then (Section 4.5.6), or will be censored at the time of insulin start (for those subjects who received rescue treatment without confirmed rescue criteria). The proportional hazards (PH) assumption of the Cox model will be visually checked (e.g., the survival curves should not cross for the PH to hold). If the PH assumption is not met, the time to rescue will be analysed using a Wilcoxon test (using SAS proc lifetest).

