The proportion of patients with at least one episode of confirmed hypoglycaemia, the proportion achieving HbA1c <7% (and <7.5%) without confirmed hypoglycaemia at week 52, the proportion achieving HbA1c <7% (and <7.5%) at week 52, the proportion achieving their individually agreed HbA1c targets at week 52, the proportion with at least one episode of any hypoglycaemia and the proportion with at least one episode of hypoglycaemia (symptomatic with blood glucose ≤70mg/dL [3.9mmol/L]) will be summarised by treatment group and compared between treatment groups using logistic regression with baseline HbA1c as a covariate (see section 4.5.7). The adjusted percentage with 95% CI, Odds Ratio with 95% CI and nominal p-values for the comparison of dapagliflozin or dapagliflozin plus saxagliptin vs glimepiride will be presented. The confidence intervals will be based on the profile likelihood method.

The proportion of patients achieving a \geq 5% weight reduction or \geq 5% weight gain will be summarised by treatment group and compared between treatment groups using logistic regression with baseline weight as a covariate.

The proportion of patients with an HbA1c decrease ≥1% with no weight gain at week 52 will be summarised by treatment group and comparisons between treatment groups (contrasts of each test combination vs the control) will be performed using a Pearson's Chi-Square test. Nominal p-values and asymptotic 95% CIs will be presented.

Descriptive summaries of change from baseline in HbA1c, FPG, weight, BMI, waist circumference and systolic BP over time (observed values), will be presented in addition to the analyses described above.

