4.11.2 Visit Windows

Deviations are to be expected between patients in the actual number of study days from randomisation to when planned visits are carried out. To handle these deviations in tables, figures, listings, and analyses, visit assessments will be slotted according to visit windows. Data will be assigned to the visit windows using study day. For the efficacy and safety data, the data will be listed and summarised by visit as listed in Table 12 below:

Table 12. Visit windows for efficacy and safety data

Visit	Target	Adjusted windows for analyses (Days)			
	Day	HbA1c	Vital Signs, sBP Body Weight, FPG*, urinalysis hypoglycaemic events	Waist circumference, BMI, ECG, complete physical examination**	Laboratory parameters***, Serum lipids
Baseline	1	≤1	≤1	≤1	≤1
Week 2	15	2 - 21	2 - 21		
Week 4	29	22 - 35	22 - 35		
Week 6	43	36 - 49	36 - 49		
Week 8	57	50 - 63	50 - 63		
Week 10	71	64 - 77	64 - 77		
Week 12	85	78 - 126	78 - 126		
Week 24	169	127 - 210	127 - 210		
Week 36	253	211 - 294	211 - 294		
Week 48	337	295 - 348	295 - 348		
Week 52	365	349 - Last dosing date ⁴ + 7	349 - Last dosing date [¥] + 4*	2 – Last dosing date of the DB period + 4	2 – Last dosing date of the DB period + 4
Follow-up Week 55	386	(Last dosing date $^{4} + 7$) – Last visit date	(Last dosing date [‡] + 4*) – Last visit date		(Last dosing date $^{\frac{1}{4}} + 4$) – Last visit date

^{*:} For FPG, week 52 and week 55 windows use last dosing date +1.

^{**:} also assessed at Week 24; **: clinical chemistry parameters also assessed at Weeks 12, 24, 36, 48.

[¥]: Last dosing date ≥ Day 349

In case of multiple observations within a single visit window, the following rules apply:

- If there are two or more observations within the same visit window, the non-missing observation closest to the target day will be used in the analysis
- If two observations are equidistant from the target day, the non-missing observation with the later collection date will be used in the analysis
- If two observations are collected on the same day and have a collection time associated with them, the non-missing observation with the later collection time will be used in the analysis
- If two or more observations are collected on the same day, all non-missing but with no collection time associated with at least one of them, the average of the observations will be used in the analysis.

If a visit window does not contain any observations, the data will be missing for that visit.

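### BMI change at Week 52 can use values from as early as Day 2 under an LOCF ANCOVA, while body weight has a Day 349 window and an MMRM

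*SAP*

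**What the plan says.** **BMI.** SAP section 4.8.2: "The change from baseline at week 52 in a) BMI and b) waist circumference will be analysed using an ANCOVA model", and "LOCF will be applied as detailed in section 4.6.2 for the latter two analyses". Section 4.6.2 defines the rule: "if no Week 52 measurement is available, the last available earlier post-baseline measurement will be used". Table 11 and planned table 42 in Appendix I also give ANCOVA with LOCF. Table 1 schedules BMI at Visits 1, 2 and 12 only, where Visit 12 is the end-of-treatment or rescue visit. Table 12 puts BMI in the waist circumference column, with a single post-baseline window labelled Week 52: "2 – Last dosing date of the DB period + 4".

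**Body weight.** Table 1 schedules weight at every visit from Visit 1 to Visit 13, and height once, at Visit 1. Section 4.8.2 says that the analysis of "changes from baseline to week 52 for a) total body weight, b) FPG and c) SBP will be performed using the MMRM model". Section 4.6.2 adds that "the MMRM model assumes missing observations are missing at random (MAR"). In Table 12 weight has ten post-baseline treatment windows, and its Week 52 window opens on Day 349.

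**Both.** Section 4.8.2 applies the same exclusions to weight, BMI and waist circumference: values after rescue, and values more than 8 days after the last dose.

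**Schedule.** Section 1.2.4.2 says that the parameters listed for baseline, which include BMI, are assessed at Visits 3 to 11. Section 4.8.2 plans "Descriptive summaries of change from baseline in HbA1c, FPG, weight, BMI, waist circumference and systolic BP over time (observed values"). Section 4.5.2 (Derived data) has no rule for BMI.

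**The concern.** With one height per patient, a patient's BMI change is that patient's weight change divided by a fixed number. The ten weights that would give BMI at every visit are already collected. The plan instead takes BMI from one scheduled value, allows that value to come from any time after Day 1, and calls it Week 52.

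At stake is what the Week 52 BMI result means. For patients who stop or are rescued early it reports an early value, taken while weight may still be changing. How far this moves the comparison depends on when patients leave each arm. A reader who compares the BMI and weight results would see differences that come partly from windowing and missing-data handling, and the SAP gives no reason for treating the two differently.

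**Working it through.** **Plan's own figure.** The SAP gives no number for BMI. Its only sample-size figure is 290 per group for HbA1c. It reproduces: 2 × (1.96 + 1.645)² × 1.0² / 0.30² ≈ 289, and power at 290 is 95.1%. It serves below only as the arm size.

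**One visit, two labels.** Take a patient who has the early-termination visit on Day 29, within 4 days of the last dose.

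| | Weight | BMI |
|---|---|---|
| Table 12 window containing Day 29 | Week 4 (Days 22–35) | Week 52 (from Day 2) |
| Use at Week 52 | Missing, handled by the MMRM under MAR | Taken as the Week 52 value |

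The window alone produces the BMI label, because LOCF is not needed to call a Day 29 value Week 52. If the patient has no eligible early-termination BMI, the Table 1 schedule leaves nothing to carry forward. The patient then drops out of the BMI analysis, although the weights stay in the weight analysis.

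**Size within one arm (assumed inputs).** Let weight change approach a plateau P with a 10-week time constant, and let early stoppers leave evenly over Weeks 2 to 51.

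- Shortfall at week t = P × exp(−t/10). The mean of exp(−t/10) over t = 2 to 51 is 0.171.
- P = 2.5 kg: 2.5 × 0.171 = 0.43 kg. P = 3.5 kg: 3.5 × 0.171 = 0.60 kg.
- With 10% to 20% early stoppers: 0.10 × 0.43 = 0.04 kg to 0.20 × 0.60 = 0.12 kg.
- At a height of 1.70 m, dividing by 1.70² = 2.89 gives 0.015 to 0.04 kg/m².

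If the arms move in opposite directions, the two shortfalls add in the comparison.

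**Size between arms (simulation, assumed inputs).** There were 60 simulated trials per scenario, with 290 patients per arm. Week 52 weight change was +1.5 kg (control) and −3.0 kg (test), with a 10-week half-time. The SD of change rose from 1.2 to 4.5 kg over the ten visits, and height was 1.69 m (SD 0.09). Dropout was unrelated to outcome, with the last visit drawn evenly from Weeks 2 to 48. The comparator was a maximum-likelihood model over all ten visits, equivalent to the weight MMRM, applied to BMI derived from each visit's weight. Shrinkage = (MMRM − LOCF) / MMRM, in absolute values. Differences are test minus control in kg/m².

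| Dropout, control / test | LOCF ANCOVA | All-visit MMRM | Shrinkage |
|---|---|---|---|
| 5% / 5% | −1.559 | −1.594 | 0.035 / 1.594 = 2.2% |
| 15% / 15% | −1.489 | −1.600 | 0.111 / 1.600 = 6.9% |
| 30% / 30% | −1.394 | −1.607 | 0.213 / 1.607 = 13.3% |
| 30% / 10% | −1.451 | −1.569 | 0.118 / 1.569 = 7.5% |

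Six of the nine possible last visits fall by Week 12, so these scenarios load dropout early.

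**The case against.** The strongest reply is that the method follows the schedule. BMI has one scheduled post-baseline value, like waist circumference, and Table 11, section 4.8.2 and planned table 42 agree on LOCF ANCOVA for both. With one post-baseline value an MMRM reduces to an observed-case ANCOVA, so changing the model alone gains nothing. This stands. A reader might infer that the SAP gives identical data two incompatible missing-data treatments, but as planned weight has ten post-baseline values and BMI has one. The case for MMRM depends on first deriving BMI at each visit.

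It is also fair that LOCF is not the only cause, since the Day 2 window does at least as much. In the simulation, where dropout was unrelated to outcome, observed-case ANCOVA was also close to the full-data result (−1.612 against −1.604 at 30% dropout). The shrinkage measures the cost of early values, not a general advantage of MMRM.

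Two further inferences go too far. Weight and BMI results need not match even under identical models, because height differs between patients. The over-time summary of BMI is not impossible, because baseline and Week 52 can be tabulated. Its Week 52 entry would, however, contain early values.

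None of this explains why the Week 52 window opens on Day 2 for BMI and on Day 349 for weight.

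**Conclusion.** The point holds as a minor, avoidable inconsistency. Early-termination and rescue-visit values enter the BMI result as Week 52 values but do not do so for weight, and the two endpoints rest on different missing-data handling without a stated reason. The passages on when BMI is assessed also disagree: Tables 1 and 12 on one side, sections 1.2.4.2 and 4.8.2 (summaries over time) on the other.

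The between-arm BMI difference shrinks by about 2% to 13% (0.04 to 0.21 kg/m²) for 5% to 30% dropout, with its direction unchanged. These figures rest on assumed weight trajectories, SDs and dropout, none of which the SAP supplies.

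A reader might infer a threat to the trial's formal conclusions. The SAP does not support that: section 4.3.1 gives other secondary variables nominal p-values outside the testing hierarchy, and body weight, the key secondary endpoint, already uses MMRM.

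**What to change.** - **Section 4.5.2:** add that BMI at each visit is that visit's weight (kg) divided by the square of the Visit 1 height (m).
- **Table 12:** move BMI to the body weight column. That column closes 4 days after the last dose, while sections 4.8.2 and 4.11.3 allow 8 days for weight, BMI and waist circumference, so align the two in the same edit.
- **Section 4.8.2, Table 11 and planned table 42:** replace LOCF ANCOVA for BMI with the weight MMRM (baseline BMI, baseline-by-week, treatment, week, treatment-by-week), keeping the same rescue and 8-day exclusions.
- **Schedule:** reconcile Table 1, section 1.2.4.2, the over-time summaries in section 4.8.2 and Table 12 on when BMI is assessed or derived.
- **Waist circumference:** ANCOVA can stay, since Table 1 schedules one post-baseline measurement. Either correct its Day 2 window or describe the result as an end-of-treatment value.

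If LOCF ANCOVA is kept for BMI, the SAP should say why and correct the window label. The cost is SAP wording and one derived variable, with no new data.

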4.3.1 Control of Type I error

The experiment-wise type I error will be controlled to a maximum of 5%. A hierarchical closed testing procedure will be employed such that key secondary endpoints will be considered for statistical significance (in terms of superiority) only if non-inferiority of the primary endpoint is concluded and that a key secondary endpoint will be considered for statistical significance only if the test ordered before it is found to be statistically significant. At each step, dapagliflozin plus saxagliptin added to metformin versus glimepiride added to metformin will be tested first followed by the test for dapagliflozin added to metformin versus glimepiride added to metformin except for the superiority tests of the primary endpoint and the endpoint of total body weight. The test of superiority for HbA1c will include only the comparison of dapagliflozin plus saxagliptin added to metformin versus glimepiride added to metformin. For total body weight, dapagliflozin added to metformin versus glimepiride will

be tested first followed by dapagliflozin plus saxagliptin added to metformin versus glimepiride added to metformin.

The following testing order will be followed for the overall type I error control:

- 1. Change from baseline in HbA1c at Week 52 (test for non-inferiority)
- 2. Proportion of patients reporting at least 1 episode of confirmed hypoglycaemia at Week 52 (test for superiority)
- 3. Change in total body weight from baseline to Week 52 (test for superiority)
- 4. Change from baseline in HbA1c at Week 52 (test for superiority of dapagliflozin plus saxagliptin added to metformin vs glimepiride added to metformin only)
- 5. Change in FPG from baseline to Week 52 (test for superiority)
- 6. Time to rescue at Week 52 (test for superiority)

The statistical comparisons will be done using a comparison-wise type I error of 5% (2-sided). For all other secondary variables and exploratory variables, nominal p-values will be reported without multiplicity controlled significance testing.

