4.5.6 Kaplan-Meier curve and estimates for time-to-event analysis

Kaplan-Meier plots of time to rescue will be displayed by treatment group. Unless otherwise specified, the plot will be presented only when there are at least 5 events in one treatment group. Additionally, a table will accompany the plot and will display the Kaplan-Meier estimates of the cumulative proportion (with 95% confidence interval based on Greenwood's method when applicable) of patients with event at specific time points by treatment group. If the estimated lower bound of 95% confidence interval is below 0 or the estimated upper bound of 95% confidence interval is over 1, then it will be restricted to 0 or 1 respectively.

Time to rescue is defined as the time (in days) from the first dose date after randomisation to the date at which the patient first meets the following rescue criterion: (which is confirmed),

- i. FPG > 240 mg/dL (13.3 mmol/L) for the period after Visit 2 to and including Visit 8 (Week 0 to 12) OR
- ii. FPG > 200 mg/dL (11.1 mmol/L) for the period after Visit 8 to and including day of Visit 9 (Week 12 to 24) OR
- iii. HbA1c > 8% for the period after Visit 9 to and including Visit 12 (Week 24 to 52)

Time to rescue will be censored at the earliest of discontinuation of study medication/study, or study completion, or time of insulin start (for those subjects who received rescue treatment without confirmed rescue criteria).

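### Time to rescue (step 6): a look at the unblinded curves, with no set criterion, decides whether the Cox or the Wilcoxon test counts, and the Cox model omits baseline HbA1c

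*SAP*

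**What the plan says.** SAP 4.3.1 puts this endpoint sixth and last in the confirmatory order: "Time to rescue at Week 52 (test for superiority"). Each comparison with glimepiride is tested at two-sided 5%, the combination arm first and then dapagliflozin.

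SAP 4.8.2 gives the method: "Time to rescue will be analysed using a Cox proportional hazards model with the Efron method (Ref 2) for handling ties". No covariate is named there, in 4.5.6 or in Table 11, which lists only a Cox model. Proportional hazards "will be visually checked (e.g., the survival curves should not cross for the PH to hold"), and then: "If the PH assumption is not met, the time to rescue will be analysed using a Wilcoxon test".

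The curves to be inspected are by arm: "Kaplan-Meier estimates will be calculated and plotted by treatment group". SAP 1.2.3 keeps the treatment codes closed until database lock, so the check can only follow unblinding.

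Under 4.5.6 the event is based on FPG up to week 24 and then on "HbA1c > 8% for the period after Visit 9 to and including Visit 12 (Week 24 to 52"). For the hypoglycaemia and HbA1c proportions, 4.8.2 has the arms "compared between treatment groups using logistic regression with baseline HbA1c as a covariate (see section 4.5.7").

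**The concern.** Two things are badly fixed.

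**The switch.** The p-value of a confirmatory step comes from one of two tests, and someone who can see the arm-level result decides which. Crossing is only an example, so other features of the plot may also count. The text does not say how large a crossing matters, or whether all three curves or only the tested pair are judged. Crossing is also a weak diagnostic: curves with proportional hazards cross by chance while they are close together, and curves that never cross can still have non-proportional hazards. The Wilcoxon test gives more weight to early events, so switching moves weight from HbA1c-triggered towards FPG-triggered rescue. It also leaves the deciding p-value without a hazard ratio that corresponds to it.

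**The covariate.** Patients enter with HbA1c between 7.5% and 10.5% and meet the rescue criterion from week 24 at more than 8.0%, so baseline HbA1c should be prognostic. The other five steps (HbA1c twice, hypoglycaemia, weight, FPG) all adjust for a baseline value. Step 6 alone does not.

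**Working it through.** **The plan's own figure.** The SAP sizes the trial on HbA1c only (1.3): margin 0.30, SD 1.0, one-sided 0.025, about 95% power. n = 2 × 1.0² × (1.960 + 1.645)² / 0.30² = 288.8, so 289 per group against 290 stated. Power at 290 is 0.951. 290 / 0.95 = 305.3, so 306 randomised per group against 310 stated. The figure reproduces. The SAP gives no rescue rate, hazard ratio or power for time to rescue, so everything below is assumed.

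**Main simulation.** Inputs from the SAP: 290 per arm, the visit grid of weeks 2 to 52 with its visit windows, entry HbA1c 7.5-10.5%, two-sided 5%. Assumed: control rescue 20-30%, HR 0.60-0.65 (constant, so hazards are proportional), 12% dropout, truncated-normal baseline HbA1c (SD 0.62), prognostic HR 1.0 to 2.5 per 1% HbA1c, events either even over time or back-loaded after week 24. There were 4,000 trials in each of 32 effect settings and 6,000 in each of 8 null settings. A crossing means that each curve lies above the other at some point.

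| Reading of crossing, hazards proportional | Trials sent to Wilcoxon |
|---|---|
| Tested pair, any crossing | 61-74% |
| Tested pair, at least 0.5 percentage points on both sides | 32-41% |
| Tested pair, at least 1 point | 18-25% |
| Tested pair, at least 2 points | 3-6% |
| Either test arm against control, any crossing | 79-89% |
| Any two of the three curves (test arms assumed equal) | 98-99% |

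The rows with a minimum size were run at prognostic HR 2.0 only. With no treatment effect the tested pair crosses in 88-92% of trials.

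**Type I error.** It is 4.4-5.1% under the literal any-crossing rule and at most 6.0% if the smaller p-value is always taken. The two tests disagree on significance in 0.7-1.5% of null trials and 2.0-3.8% of trials with an effect.

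**Power of the full change** (one fixed test plus baseline HbA1c) against the literal rule:

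| Prognostic HR per 1% HbA1c | Gain, percentage points |
|---|---|
| 1.0 | 0.2-1.3 |
| 1.5 | 0.7-1.8 |
| 2.0 | 1.7-3.6 |
| 2.5 | 3.3-6.1 |

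Example (control 30%, HR 0.65, prognostic HR 2.0, even events): literal rule 0.670, Cox always 0.677, Wilcoxon always 0.675, adjusted Cox 0.706. Removing the switch gives 0.677 - 0.670 = 0.7 points, and the covariate gives 0.706 - 0.677 = 2.9 points. At prognostic HR 1.0 the literal rule, unadjusted Cox and adjusted Cox give 0.689, 0.701 and 0.702: 1.2 points from the fixed test and 0.1 from the covariate.

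**Second simulation, other assumptions.** Rescue 10-30%, HR 0.70, 10% dropout, events exactly at the visits without windows, 200,000 trials per setting. Any crossing occurs in 49-66% of trials, and crossing from week 12 onwards in 19-45%. Type I error is 4.7-4.9% under the literal rule and 5.2-5.5% with free choice. For the covariate (HR 0.65, baseline SD 0.8, 2,000 trials per setting), power goes from 0.55 to 0.56 and from 0.70 to 0.72 at log HR 0.5 per 1% (20% and 30% rescue). At log HR 1.0 it goes from 0.47 to 0.53 and from 0.64 to 0.73, and the unadjusted hazard ratio is pulled to 0.67-0.68. Leaving out the visit windows accounts for most of the gap in crossing rates: a further run under proportional hazards gave 68-73% with windows and 42-57% without.

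**Non-proportional hazards** (control 30%, 12% dropout, HR changing at week 24, unadjusted tests):

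| HR before, then after week 24 | Cox | Wilcoxon | Literal rule |
|---|---|---|---|
| 0.45, then 1.0 | 0.52 | 0.60 | 0.53 |
| 0.85, then 0.5 | 0.60 | 0.54 | 0.55 |

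In both rows the literal rule lands close to the weaker test. With HR 0.4 then 0.9, a clear violation, the curves cross in only 16-37% of trials, against 40-53% in the same set-up with a constant HR of 0.65.

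**The case against.** The best defence is that little is at stake. The SAP fixes a default, a check and one named fallback, and it does not permit picking the smaller p-value, so the 6.0% ceiling is hypothetical. Type I error under the literal rule is essentially nominal, the tests seldom disagree, and the step is last. This stands, and it limits the severity.

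The high crossing rates assume that any crossing counts, which the SAP does not say. That is fair, and the fall from 61-74% to 3-6% shows how far the answer depends on the reader. But it is the absence of a stated reading that leaves the range so wide.

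An unadjusted Cox test is valid in a randomised trial, the SAP is silent on covariates rather than ruling them out, rescue before week 24 depends on FPG, and one secondary proportion (an HbA1c fall of at least 1% without weight gain) is tested by an unadjusted chi-square. All true. The covariate is a matter of power and consistency, not of error control. The chi-square endpoint, however, lies outside the hierarchy.

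The rescue criterion changes at weeks 12 and 24, so non-proportional hazards are plausible and the Wilcoxon test could be the stronger one. This also stands: neither test dominates. It is a reason to choose one in advance, not to choose by eye.

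Finally, 4.8.2 also promises a hazard ratio with its interval, and this may still be reported after a switch. It would then not be the quantity behind the deciding p-value, and the two could disagree.

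**Conclusion.** The concern holds. The confirmatory test for step 6 is left to an unblinded visual judgement without a criterion, and the one example given would often reject a valid Cox analysis if taken literally. Baseline HbA1c is left out of the only unadjusted step in the hierarchy.

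The size is modest. Type I error rises by at most 1.0 point, and only if the smaller p-value is always taken. The tests disagree in at most 3.8% of trials under proportional hazards. The unused power is 0.2-6.1 points, most of it from the covariate when the prognostic HR is 2.0 or more per 1%. These figures rest on assumed rescue rates, hazard ratios and prognostic strength, because the SAP supplies none. That the choice is unfixed does not depend on them. It should be corrected before unblinding, but it does not threaten the primary conclusion or any other step.

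**What to change.** In SAP 4.8.2 and Table 11, name one confirmatory test for each step 6 comparison with glimepiride: a Cox model with treatment and baseline HbA1c, Efron ties. State that its p-value and hazard ratio are the step 6 result whatever the curves look like. Keep the Kaplan-Meier estimates, a residual-based check of proportional hazards and the Wilcoxon test as supportive analyses that cannot replace it.

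The cost is a wording change and one covariate already collected. There are two small downsides: under non-proportional hazards the hazard ratio is a time-average (and Wilcoxon would be stronger for an early benefit), and the adjusted hazard ratio is conditional on baseline HbA1c. This settles the test only. The event definition, which differs between 3.2 and 4.5.6, needs separate attention.
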